Two randomized effectiveness trials have demonstrated MATCH's effectiveness against usual care and standard treatment protocols (Cohen's d s from .47 to .55)⁴³⁻⁴⁴. MATCH draws from various domains of evidence-based treatment and consists of 33 treatment modules. There are several core module sequences for problem areas such as depression, anxiety, trauma, or disruptive behaviour and a clinician can utilize these sequences based on the primary concern for the individual. MATCH treatment usually ranges from 4 – 6 months, but the duration is flexible and dependent on the individual's needs. If an individual reports additional stressors or comorbid conditions, the clinician can modify the sequence of the modules to address these comorbidities. For example, if a child has been referred for the treatment of conduct problems, the clinician may utilize behavioural parent training, rewards, and time outs. If the child were to further report depressive symptoms, the clinician could incorporate modules from the depression pathway, such as problem solving and cognitive restructuring. MATCH treatment is flexible and can be tailored for each individual, so it is highly effective⁴⁵.

Clinicians administering MATCH-ADTC treatment will be asked to complete a Therapist Background Questionnaire⁴⁶, which asks about their training, educational background, and experience with child psychotherapy. They will have regular team meetings with the principal investigators ([name], [name], [name]) to discuss the implementation of the MATCH treatment program. These consultation meetings – which will not entail clinical supervision – are to support the implementation of MATCH with high fidelity. Brief consultation notes will be documented. All information shared at these meetings will be de-identified and personal health information will only be discussed on an as needed basis (e.g. age, sex, mental health concerns). To establish treatment alliance, adherence, and fidelity, therapy sessions will be audio recorded. A randomly selected 20% of the sessions will be coded for fidelity using the Therapist Integrity in Evidence Based Interventions and Therapy Process Observational Coding System – Alliance Scale⁴⁷. Clinicians will complete weekly session notes and fidelity checks, and at discharge of each MATCH-ADTC client, clinicians will complete the *Therapist Satisfaction Index*⁴⁸.

Control Group

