Previous studies involving randomized waitlist controlled studies have established that MATCH-ADTC treatment is more effective than usual care. The justification of the control arm in this study is to allow us to evaluate the changes in biobehavioural regulation as a consequence of MATCH-ADTC treatment. The waitlist control exists to support our hypothesis that changes in emotion regulation are not merely due to the passage of time or normal emotional/psychological development in children.

The control arm of this project will consist of a no-treatment, waitlisted group. Participants in the waitlist condition will remain on the waitlist for standard usual care, and the estimated wait time is approximately 4-9 months. While in the waitlist control arm, participants are required to complete 75% of the weekly measures and attend both the quarterly (3-month) and the post-test study visit. If participants decide not to continue with the study, or they are lost to follow-up, they will be considered a drop-out in the Big Feelings Study, but their referral will remain open for usual care and they will remain on the clinic waitlist. Upon completion of the post-assessment, participants in the waitlist condition will be offered a bridging treatment (usually MATCH-ADTC treatment) until their usual care standard treatment spot becomes available, at which point they can decide whether they would like to continue with the bridging treatment or move to the standard care. Therefore, participants assigned to the control arm will also receive high quality, evidence-based treatment.

Compensation

Children and their parent(s)/caregiver(s) will be compensated for their participation. They will be provided with gift cards at each study visit and for completion of the weekly surveys. If participants are only able to complete the questionnaires, they still receive a portion of honorarium (see table, where the amount for “questionnaires” indicate how much participants can receive as honorarium for partial completion).

	Pre-Test Visit	Weekly Surveys	Quarterly Visit(s)	Post-Test Visit	
Parent	\$30 questionnaires only \$40 both questionnaires and in person visits	\$2 per survey \$5 bonus for every 5 completed	\$30 questionnaires only \$40 both questionnaires and in person visits	\$30 questionnaires only \$60 both questionnaires and in person visits	

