Preliminary analyses will test for significant differences in demographic factors between the MATCH and waitlist groups; significant factors will be covaried in our models. In the unlikely event that medication discrepancies are discovered between the two treatment groups, we will equate the groups by imposing propensity scores-based weighting in the analysis. An exploratory factor analysis (EFA) will examine whether the emotion regulation variables load onto a broad latent construct. Variables that do not load on the same factor will be examined independently within our mediation models. Latent Growth Curve (LGC) mediation modeling, which will account for the nested structure of the data as well as potentially unequally spaced time points, will test whether improvements in emotion regulation mediate improvements in symptoms as a result of MATCH treatment. We will conduct two types of mediation analyses corresponding to our operationalization of treatment response – pre-post change and trajectory of change. First, emotion regulation (latent biobehavioural regulation factor(s) from the EFA) will be modeled as a latent change from baseline to the 3-month quarterly assessment, and symptom change (CBCL/YSR internalizing and externalizing scores) will be modeled as a latent change from baseline to the post assessment. Our predictor will be specified as MATCH vs. Waitlist to ensure we can derive conclusions about the impact of MATCH on emotion regulation and symptoms. To test the mediated effect, we will apply the recommended bootstrap-based product of coefficients, which will yield bias-corrected 95% CIs based on the recommended asymmetric CI method. Second, to understand trajectories of change during MATCH treatment, we will apply LGC modeling to examine latent slopes of change in emotion regulation (weekly CADS) and symptoms (weekly BFS) and explore the temporal relations between the two trajectories. This will allow us to understand the temporal order and bi-directionality of changes in regulation and symptoms. In both modeling approaches, we will co-vary child age, gender/sex, medication use, puberty status, ethnicity, and treatment fidelity. We will apply an intent-to-treat approach and full information maximum likelihood estimation to account for potential bias caused by missing data.

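### The MATCH-versus-waitlist mediation model adjusts for treatment fidelity, which no waitlisted child can have

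*Protocol*

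**What the plan says.** All of the modelling text is in the protocol's Data Analysis section. Two approaches are described. In the first, latent change in emotion regulation from baseline to the 3-month visit mediates latent change in symptoms from baseline to the post assessment, and "Our predictor will be specified as MATCH vs. Waitlist". The second uses the weekly scales "to understand trajectories of change during MATCH treatment". One sentence then sets the adjustment for both: "In both modeling approaches, we will co-vary child age, gender/sex, medication use, puberty status, ethnicity, and treatment fidelity". The next sentence states "We will apply an intent-to-treat approach", with full information maximum likelihood for missing data.

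Fidelity is described only under MATCH Treatment: "To establish treatment alliance, adherence, and fidelity, therapy sessions will be audio recorded", and "A randomly selected 20% of the sessions will be coded for fidelity". Clinicians also complete weekly fidelity checks. No fidelity rating is described for anyone outside MATCH.

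Under Control Group: "The control arm of this project will consist of a no-treatment, waitlisted group". Any exposure of that arm to MATCH comes later: "Upon completion of the post-assessment, participants in the waitlist condition will be offered a bridging treatment". Data Collection likewise places the waitlist post visit before the child is taken off the waitlist for usual care.

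**The concern.** The covariate sentence covers both approaches, so it includes the model whose predictor is the randomised arm. Fidelity is a property of therapy that was delivered. It arises after randomisation and exists in one arm only. A child on the waitlist has no sessions to rate between baseline and the post assessment, and a child allocated to MATCH who never starts would have none either.

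The path from MATCH to emotion regulation is half of the mediated effect that Aim 1 tests and that the 168 analysable children were sized to detect. If the list is followed literally, that path is either lost or changes meaning, depending on how the empty waitlist values are filled. Neither result answers the intent-to-treat question of what assignment to MATCH does.

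**Working it through.** **Inputs from the protocol (Sample Size).** Treatment effect d = 0.5, alpha 0.05, beta 0.2, 25% mediated, N = 168.

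**Assumptions.** 1:1 allocation (84 per arm), a two-sided test, and outcome residual SD 1. The protocol gives no fidelity mean or SD, so four combinations were used: mean *m* = 4 or 5, SD *s* = 0.6 or 1.2.

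**Planned power.** The mediated effect is 0.25 × 0.5 = 0.125. The protocol does not give the two paths. With a = 0.5 (arm to regulation) and b = 0.25 (regulation to symptoms), simulation at N = 168 gives power of 81% with a Monte Carlo interval for the product, and 80% with a joint significance test. That agrees with the plan, but only for this split. With a = 0.3, 0.4, 0.45 and 0.6, and b = 0.125/a, the joint test gives 50%, 73%, 75% and 77%. For the total effect without fidelity, SE = sqrt(2/84) = 0.154 and power is 90%.

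**Coding 1: waitlist fidelity missing.** If fidelity is an exogenous covariate, only MATCH children remain. The arm indicator is then constant, and the design matrix (intercept, arm, fidelity) has rank 2 of 3, so the arm effect is not estimable. Full information maximum likelihood does not restore it: mean fidelity on the waitlist is never observed, so the arm effect given fidelity is not identified.

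**Coding 2: waitlist fidelity set to 0.** The fidelity slope is estimated within MATCH alone, and the arm coefficient compares the MATCH line at zero fidelity with the waitlist mean:

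- arm coefficient = 0.5 − slope × *m*
- SE = sqrt((2 + (*m*/*s*)²)/84)
- correlation of fidelity with arm = 1/sqrt(1 + 2(*s*/*m*)²)

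For *m* = 4, *s* = 1.2: SE = sqrt((2 + 11.11)/84) = 0.40. For *m* = 5, *s* = 0.6: SE = sqrt((2 + 69.44)/84) = 0.92. Simulation used 4,000 replicates per row for the total effect and 1,500 for the mediated effect. Both power columns assume that benefit does not vary with fidelity (slope 0).

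| *m*, *s* | Correlation with arm | SE, formula | SE, simulated | Power, total effect | Power, mediated effect |
|---|---|---|---|---|---|
| 4, 1.2 | 0.92 | 0.40 | 0.40 | 24% | 20% |
| 5, 1.2 | 0.95 | 0.48 | 0.49 | 18% | 16% |
| 4, 0.6 | 0.98 | 0.74 | 0.75 | 10% | 9% |
| 5, 0.6 | 0.99 | 0.92 | 0.93 | 9% | 7% |

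If benefit is proportional to fidelity, slope = 0.5/*m* and the coefficient is 0.5 − 0.5 = 0. Power is then about 5% for the total effect and 4-5% for the mediated effect.

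A second simulation put fidelity on a 0-1 scale (mean 0.6-0.8, SD 0.1-0.2, slopes 0 to 1). Estimates ran from −0.33 to 0.49 against a true 0.50, SEs were 0.37-0.90, and rejection rates were 5-19%.

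**Coding 3: fidelity centred within MATCH, waitlist set to 0.** The arm estimate is 0.50 with SE 0.154, and power for the mediated effect is 79-82%. Nothing is lost.

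**The case against.** The strongest reply is that the harm comes from the coding and not from listing the covariate. Centring within MATCH leaves the arm effect intact, and coding of structurally absent values normally belongs in the SAP, which is not at hand. It is true that centring is harmless. But the protocol itself commits the between-arm model to this covariate without qualification. A SAP that applies the list plainly inherits the fault, and centring would only neutralise a term that contributes nothing to the randomised contrast.

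The size of the loss rests on assumed fidelity values, on one split of the mediated effect, and on an observed-variable model with a Monte Carlo interval in place of the latent-change model with a bias-corrected bootstrap. That stands. The near-zero estimate under proportional benefit also follows by construction; it shows what the coefficient means and does not forecast the trial's result. However, neither the loss of identification nor the zero-fidelity meaning depends on those values.

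Under coding 2 every randomised child stays in the model as assigned, so the conflict with intent-to-treat lies in what the coefficient means and not in who is analysed. That is also fair.

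Finally, no data are lost, the list can be corrected at any time before analysis, and coding 1 would reveal itself as a model that cannot be fitted. Uncentred zero coding gives no such warning: it yields a plausible-looking but uninformative result.

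**Conclusion.** The concern holds for the MATCH-versus-waitlist mediation model and must be corrected before analysis. As written, the adjustment makes the arm effect inestimable (waitlist missing) or turns it into an extrapolation to zero fidelity (waitlist 0). In the second case the standard error is about 2.6 to 6 times the unadjusted one (0.40/0.154 to 0.93/0.154), and power for the mediated effect is at most about 20% against a planned 80%. These sizes assume 84 per arm, a = 0.5 and b = 0.25, and the fidelity values above. The direction of any bias depends on how benefit relates to fidelity, which the protocol does not give.

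The objection does not extend to the weekly trajectory model if that is run within MATCH, where fidelity is usable.

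**What to change.** In Data Analysis, split the covariate sentence. Keep the other listed covariates for both approaches, and state that treatment fidelity enters only secondary analyses within the MATCH arm (including the weekly trajectory model if that is confined to MATCH) and no model containing the MATCH-versus-waitlist contrast.

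A related clarification belongs in Covariates. Number of sessions attended is named there as a control variable without saying in which model, and it would cause the same difficulty only if it entered the between-arm model. One clause restricting it to MATCH-arm analyses settles this.

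The cost is one reworded sentence and one added clause. No new data are needed, and both fidelity and sessions remain available within MATCH.

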If a family is eligible and interested in study participation, the research staff will document this in their clinical chart after the initial screening. All referrals to the Better Behaviours Service are maintained on a clinic waitlist, and referrals to the Mood & Anxiety Clinic are maintained on two waitlists: individualized treatment and group treatment. After participants provide informed consent, they will be enrolled into the study. Research notes will be generated and added to their clinical charts identifying their participation in the study as well as which condition they have been assigned to. Additionally, their status in the study (e.g. waitlisted for MATCH-ADTC, waitlisted for treatment, currently in treatment), will be identified on the clinic waitlists at the Better Behaviours Service and Mood and Anxiety Clinic. The study investigators are clinicians at both clinics so they have oversight of the clinic waitlists. Clinicians at the Better Behaviours Service and the Mood and Anxiety Clinic will also be involved with administering MATCH-ADTC treatment and treatment as usual, so they will also generate notes for the patient’s clinical charts.

Study Inclusion/Exclusion

Children aged 8 – 15 will be screened for a primary diagnosis of anxiety, depression, or disruptive behaviour prior to study enrollment. Parent(s)/caregiver(s) will report on their child’s symptoms, behaviours and functioning using the Child Behavior Checklist (CBCL). Children aged 11 – 15 will complete the CBCL and the Youth Self Report (YSR). A diagnostic profile will be generated and reviewed to determine if the child meets the criteria for a primary diagnosis of anxiety, depression, or disruptive behaviour. Comorbidity is expected, and children with comorbid diagnoses will be included

in the study. Children who meet the criteria for psychosis, schizophrenia spectrum disorders, eating disorders, or autism spectrum disorders will be excluded. Children with low cognitive functioning or lack of English proficiency that would prevent active participation in research tasks will be excluded from this study. Finally, children who report current suicidality and require immediate hospitalization for suicide risk will also be excluded. If a child does not assent to participation, we will not include the family in the study.

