Videos will be recorded using an ipadaudio will be recorded via a digital recorder for the purpose of transcription, qualitative coding and fidelity checks. Recordings will be transferred via secure file transfer to the research team at the University of Guelph for transcription and coding. Once transferred, the video and audio recordings on the devices will be deleted from the recording devices and will be stored on encrypted hard drives at CAMH and secure servers at Guelph. The folder containing all video/audio recordings will be accessible only to members of the research team who have received appropriate training. Video and audio recording files will be retained at both sites for 10 years.

Once a participant agrees to participate in this study and signs the consent form, a research note will be generated on their medical record.

Participant Randomization

Stratified randomization by gender (boy, girl and non-binary) and age group (ages 8 – 10, 11 – 13, 14 – 15) will be employed to ensure balance in sample size between treatment and control groups with regard to gender and age randomization. REDCap will be employed and will allocate the participants based on a computer-generated randomization list using random block sizes. Allocation concealment will be achieved since the person making this assignment will have no awareness or control over the randomization schedule.

Data Collection

Measurement for this study will be multi-modal and will consist of questionnaires for the parent(s)/caregiver(s) and child, behavioural/cognitive tasks, a parent-child interaction task, and physiological measures. Data collection will be conducted by trained research staff with the supervision of the study investigators. The study investigators will conduct regular meetings with the

Parent and child questionnaires will be administered electronically via REDCap. In order to ensure consistency between the two sites (CAMH and Guelph), we will use a shared REDCap Project to administer questionnaires to participants. REDCap questionnaires, behavioural/cognitive tasks, parent-child interaction task, and physiological measures will be completed at each study visit. Additionally, parents and children will complete brief weekly questionnaires via secure, encrypted links from REDCap.

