CCNES³⁹: The Coping with Children's Negative Emotions Scale is a self-report assessment which presents parent(s)/caregiver(s) with hypothetical scenarios in which their child is upset or angry (e.g. My child falls off their bike and breaks it, then gets upset and cries). Each scenario provides 6 possible responses to the child's distress and the parent(s)/caregiver(s) are asked to rate their likelihood of utilizing that response. Each response represents a different way of responding to a child's distress. It will be completed by the parent(s)/caregiver(s) of the child at pre- and post-test, and follow up.

Covariates

Prior to treatment, demographic information (e.g. child's age, sex, gender identity, ethnicity, language) will be provided by the child's parent(s)/caregiver(s). Demographic information is important for data analysis purposes and will allow us to identify any different patterns of treatment responses in different groups (e.g. treatment response in male children compared to treatment response in female children). Parents will report on their country of birth and their child's country of birth, as parents and children born outside of Canada often face immigration difficulties, cultural adjustment issues, and language barriers. Additionally, this allows us to evaluate the representativeness of our sample compared to the Canadian population. Information will be collected from the participants' health record on the number of sessions attended, and will be included as a control variable.

The parent(s)/caregiver(s) and child will report on the child's pubertal development, as indicated by the Tanner Stages Assessment⁴⁰. Information on pubertal development is needed because puberty can influence the physiological measures of emotion regulation being used in this study (e.g., heart rate variability). Parent(s)/caregiver(s) will report on their child's medication status pre- and post-test, at follow up, and quarterly during the course of treatment. To assess for satisfaction with treatment, parent(s)/caregiver(s) will complete the Youth Services Satisfaction Survey for Families⁴¹⁰.

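### The stated covariates for both mediation models omit the child's primary problem, which leaves the path from regulation change to symptom change open to confounding by problem group

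*Protocol*

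**What the plan says.** All references are to the protocol.

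- **Study Inclusion/Exclusion.** Children "will be screened for a primary diagnosis of anxiety, depression, or disruptive behaviour prior to study enrollment". Several problems in one child are allowed: "Comorbidity is expected, and children with comorbid diagnoses will be included".
- **Data Analysis, fixed covariates.** For both modelling approaches (pre-post latent change and weekly trajectories), "we will co-vary child age, gender/sex, medication use, puberty status, ethnicity, and treatment fidelity".
- **Data Analysis, screened covariates.** Preliminary analyses will "test for significant differences in demographic factors between the MATCH and waitlist groups", and factors that differ are added. The screen covers demographic factors only.
- **Covariates.** Health records will supply the "number of sessions attended, and will be included as a control variable".
- **Participant Randomization.** "Stratified randomization by gender (boy, girl and non-binary) and age group" is planned; primary problem is not a stratum.
- **MATCH Treatment.** The clinician can choose the module sequence by the child's primary concern and can modify it for comorbid conditions.
- **Rationale and Study Objectives.** The primary objective is to test regulation of negative emotion as a mechanism of change that cuts across diagnoses. Moderators are mentioned as a possible further question, with no variable named.

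**The concern.** A mediated effect is the product of two paths: arm to regulation change (a), and regulation change to symptom change given arm (b). Randomisation protects a and the total effect of arm on symptoms. It does not protect b, because nobody is randomised to a degree of regulation change. A baseline variable related to both changes biases b unless it is in the model.

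Primary problem is an obvious candidate, and the protocol itself gives reasons to think so. The weekly CADS, the regulation measure in the trajectory model, was developed around propensity to conduct disorder, and its negative-emotionality items describe angry responses to frustration. The reward task is said to relate to depression at one end and to behaviour problems at the other. The outcomes are internalizing and externalizing change, the axis along which the primary problems differ. Treatment content can follow the primary concern. The protocol justifies recording puberty because it can influence the physiological measures, and the same reasoning applies to primary problem.

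If problem groups change at different rates on both sides, part of b reflects which problem the child has. A mediated effect could then be inflated, or a real one masked, in the analysis that carries the primary objective.

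**Working it through.** **1. Anchor from the plan's own figures.** The Sample Size section gives d = 0.5, α = 0.05, β = 0.2, 25% mediated and N = 168. It does not state a and b. With total effect 0.5 and 25% mediated, a × b = 0.125. Taking a = 0.5 gives b = 0.25, and simulated joint-significance power at N = 168 is 0.82, so the planned 80% is reproduced on that reading. The value b = 0.25 is used below.

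**2. Assumed inputs (not in the protocol).** One observed mediator; a share p = 0.4 of children in one problem group (G = 1); residual SD 1. That group is shifted by g SD on both changes:

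M = 0.5X + gG + e₁, Y = 0.375X + bM + gG + e₂, where X is arm.

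**3. Same shift in both arms, G omitted.** Bias in b = v/(1 + v), with v = g²p(1 − p) = 0.24g². For b = 0, the rejection rate of a two-sided 5% test is approximated with SE(b) ≈ 1/√168 = 0.077.

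| g | v | bias in b | share of b = 0.25 | rejection if b = 0 |
|---|---|---|---|---|
| 0.3 | 0.0216 | 0.021 | 8% | 6% |
| 0.4 | 0.0384 | 0.037 | 15% | 8% |
| 0.5 | 0.0600 | 0.057 | 23% | 11% |
| 0.6 | 0.0864 | 0.080 | 32% | 18% |

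Simulation with 4000 replicates per cell gave 6%, 7%, 11% and 18% for the test of b. With G in the model the rate returned to about 5%. The protocol tests the product of paths; using joint significance as a stand-in for its bootstrap interval, the rates were 5.2%, 6.6%, 10.6% and 15.8%.

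**4. Shift only in treated children, G omitted.** This matches a difference that arises through module choice. Half the sample carries the shift, so v is halved to 0.12g². At g = 0.3 the bias is 0.0108/1.0108 = 0.011; at g = 0.6 it is 0.0432/1.0432 = 0.041. As a share of b = 0.25 that is 4% to 17%. The rejection rate under b = 0 is about 5% to 8%.

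**5. What a main effect of G leaves behind in step 4.** Once X and G are in the model, the unmodelled part is (G − p)(X − ½), with variance p(1 − p)/4, so v = 0.06g². The remaining bias is 0.0054/1.0054 = 0.005 at g = 0.3 and 0.0216/1.0216 = 0.021 at g = 0.6, about half of step 4. Adding the G-by-arm term removes it under this model.

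**6. Opposite signs.** If the group is shifted by +g on one change and −g on the other, the biases in steps 3 and 4 change sign and b is understated.

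**7. Cross-check with three groups.** With three equal groups and a standardised effect r on both changes (n = 200,000, true b = 0.25), omitting the factor gave b of about 0.26, 0.29 and 0.35 for r = 0.1, 0.2 and 0.3. The formula r²/(1 − 0.0625) gives biases of 0.011, 0.043 and 0.096, in agreement. The a path and the total effect stayed at about 0.50 throughout, and adding the factor restored b to 0.25.

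**The case against.** The strongest case against is that nothing here is a contradiction. The protocol never shows that problem groups differ in both changes, and baseline severity, trauma or site could be named as confounders just as easily. The covariate sentence is also not exhaustive, since sessions attended is added elsewhere, and an analysis plan not at hand could add more. This stands in part: the size of the bias is unknown and the list could be extended. But the protocol does specify the covariates for these models, and primary problem differs from other candidates in being the entry criterion, a guide to treatment content and the subject of the cross-diagnostic claim.

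Four further readings are tempting and are not supported.

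- **That the randomisation strata are at fault.** Stratifying on primary problem would balance the arms. It would not remove confounding of b.
- **That primary problem is wholly uncontrolled.** Outcomes in the first model are latent changes from baseline, which removes stable level differences between groups. Only differences in change can confound.
- **That the label dictates treatment or clinic.** The MATCH Treatment section leaves the sequence to the clinician, and recruitment also draws on a psychiatric assessment waitlist and on a second site with no such split described.
- **That the larger figures are expected.** They need same-sign shifts in both arms. Internalizing and externalizing outcomes may well shift in opposite directions, and a treatment-only shift halves the bias.

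**Conclusion.** The point holds as an avoidable weakness in the stated covariate set, confined to the mediator-to-symptom path and therefore to the mediated effect. Under assumed same-sign shifts of 0.3 to 0.6 SD in both arms, the bias in b is about 0.02 to 0.08. It is small at the low end, about half as large if the shift exists only under treatment, and negative if the signs differ. These values rest on an assumed 40% group share, a single observed mediator and a true b of 0.25; none of the shifts comes from the protocol.

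A reader might infer that the treatment comparison itself is compromised. It is not: the total effect and the arm-to-regulation path remain unbiased. A reader might also infer that adjustment would show the mechanism to hold within each problem group. It would not; that needs an interaction or subgroup analysis, which the protocol leaves open under moderators.

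**What to change.** In Data Analysis, add primary problem as determined at screening (anxiety, depression, disruptive behaviour; or internalizing versus disruptive if a group is small) to the covariates of both mediation models, in both the mediator and the outcome equations. Add a sensitivity analysis with an arm-by-primary-problem term, because a main effect alone leaves about half of any treatment-only bias in place.

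The cost is one or two degrees of freedom in the main models and a little extra analysis. It also needs a written rule for coding one primary category per child: the protocol has a diagnostic profile reviewed at screening and expects comorbidity, but does not say that a single exclusive label is stored. Randomisation, sample size and data collection stay as they are.
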